## 9. BIOMETRY

In the context of organizational feasibility, descriptive data is reported and visualized for robot-assisted VEM. Subsequently, regression analyses are used to contextualize and quantify the data. Depending on the variables and the type of distribution, they are quantified after calculating degrees of freedom and correlations are tested using applicable analysis methods.

Descriptive data on stress experience and physical behavior will be collected within a robot-assisted mobilization situation and analyzed and visualized using descriptive statistics.

Within the study population, conventional early mobilization of critically ill intensive care patients (historical comparison group) will be compared with robot-assisted early mobilization. The data will be evaluated by graphical representations of the individual parameters in the course by means of box plots and scatter diagrams. Associations between parameters are quantified using appropriate (depending on scale level and distribution) correlation coefficients. For comparison between conventional and robot-assisted VEM, commonly used robust statistical methods are applied.

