## 6. STUDY DESIGN

The present study is a monocentric, prospective intervention study, designed to

- evaluate the feasibility and integration in the setting of an Intensive Care Unit.
- evaluate the behavior and experience of the mobilizing specialists of the robot-assisted VEM in a longitudinal section (three data collection points).
- compare robot-assisted VEM in critically ill intensive care patients with non-robot-assisted early mobilization according to the standard of care of a historical patient population.

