#### *Exclusion criteria*

- Patients refusal to participate in the study
- unable to give informed consent
- chronically bedridden before inclusion
- clinical frailty scale  $\geq 7$  (42)
- chronic ventilation (more than 24 hours) before admission to the intensive care unit
- Elevated intracranial pressure / risk for elevated intracranial pressure / recent cerebral hemorrhage
- Pregnancy
- Pre-existing neuromuscular disease resulting in chronic limitation of strength and performance
- Sternotomy / Sternectomy during a surgical procedure

Patients meeting the following criteria will be retrospectively selected for the historical comparison group:

- planned surgical procedure
- Postoperative intensive care and therapeutic treatment
- Duration of ventilation > 48 hours
- age  $\geq 18$  years
- Weight >45 kg and <135 kg
- Body height >1.50 m and <1.95 m
- Patients who met any of the exclusion criteria during their intensive care unit stay will not be included in the historical group.

No matching is planned.

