### 7.3. NUMBER OF PATIENTS

In order to test correlations using multiple-variate models (multiple linear regressions) with a statistical power of 80% on approximately 8 independent variables (UV) compared to the dependent variable (AV), an approximate total sample size of 50 subjects is required.

Thus, with an expected drop-out of 10%, 55 patients (robotic intervention and historical comparison group) should be included in the study. A sample size of 20 subjects is considered a lower limit with moderately strong associations between UVs and AV and inclusion of a maximum of 5 UVs, with  $\alpha=5\%$  and  $\text{power}=80\%$  (43, 44). In this regard, if 30-35 patients are included in the robot-assisted intervention and a maximum of 6 UVs, meaningful results can be expected to be obtained in a manageable period of time.

All patients will be included in the intervention only if written informed consent is obtained. Due to the expected patients' recruitment (6-8 patients/month) with a given number of cases (30-35 patients in the intervention), the study is expected to last five to six months from the start. The recruitment rate depends on the number of patients.

In general, all patients meeting the above-mentioned criteria will be included in the study. The study is completed as soon as the required number of patients has been recruited for the intervention. The corresponding number of cases for the historical group will be taken from the routine data.

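### Section 9 fixes no control of confounding for the unmatched robot-versus-historical comparison and does not carry through the regression on which section 7.3 sizes the study

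*Protocol*

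**What the plan says.** Four places in the protocol bear on this.

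- **Section 6 (Study design)** sets the aim of the third arm: to "compare robot-assisted VEM in critically ill intensive care patients with non-robot-assisted early mobilization according to the standard of care of a historical patient population". The control is neither concurrent nor randomised.
- **Section 7.2 (criteria for patients)** selects the historical group retrospectively, under nearly the same eligibility limits, and ends: "No matching is planned".
- **Section 7.3 (Number of patients)** bases the sample size on "multiple-variate models (multiple linear regressions") at 80% power with about 8 independent variables, and concludes that "an approximate total sample size of 50 subjects is required". That becomes 55 after 10% drop-out, explicitly counting both groups. Lower limits of 5 and 6 independent variables are also mentioned. None of the variables is named, and the section does not say that treatment group is one of them.
- **Section 9 (Biometry)** mentions regression once, in the paragraph on organisational feasibility of the robot treatment: "Subsequently, regression analyses are used to contextualize and quantify the data". For patient outcomes it gives box plots, scatter diagrams and correlation coefficients, and then, for the comparison itself: "For comparison between conventional and robot-assisted VEM, commonly used robust statistical methods are applied".

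No section mentions covariate adjustment, weighting, a propensity score or stratification for robot versus historical.

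**The concern.** The two groups arise in different ways. Robot patients are able to consent, are informed before surgery and agree to take part. Historical patients are picked afterwards from routine records. Differences in severity, age or diagnosis between the groups could enter the estimated effect, and neither randomisation nor matching guards against that. The only remaining tool is the analysis, and the sentence in section 9 that governs the comparison does not call for adjustment.

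Two people following the protocol could reach different analyses. Someone working from section 9 could run a rank test on two groups and be compliant. Someone working from section 7.3 would fit a multivariable model. If the choice is left open until the data are seen, it can be influenced by the results.

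The stakes are practical. Ventilation time is a primary outcome in section 4.3, and section 10 foresees rapid adoption in routine care if robot-assisted mobilisation proves better than the historical standard.

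**Working it through.** **1. The plan's own figure.** Section 7.3 gives 50, inflated to 55.
- Drop-out: 50 x 1.1 = 55; 50 / 0.9 = 55.6, rounded up to 56. The stated 55 is consistent.
- The 50 cannot be reproduced, because no effect size is given for it. The overall F test with 8 predictors (noncentral F, noncentrality f² x N, alpha 5%) has 80% power at N = 50 only if f² = 0.36, that is R² = 0.36 / 1.36 = 0.26. Under assumed values, f² = 0.35 needs N = 52 and f² = 0.15 needs N = 109.
- What matters here is that the figure belongs to a multivariable regression over both groups, not to a two-group test.

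**2. Sections 7.3 and 9 side by side.**

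| | Section 7.3 | Section 9, patient outcomes |
|---|---|---|
| Method | Multiple linear regression | Plots, correlations, unnamed robust methods |
| Independent variables | About 8, or at most 5 or 6 | None mentioned |
| Patients | Robot and historical together | Robot against historical |

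Section 9 does not exclude the section 7.3 model, but it does not adopt it for these outcomes either.

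**3. What uncontrolled confounding could do.** The protocol gives no figure for imbalance or for prognostic strength, so both are assumptions.
- Inputs: 30 v 30 (section 1); one baseline severity measure; systematic imbalance 0.3 to 0.5 SD (assumed); correlation with the outcome 0.3 to 0.5 (assumed); no true effect; no adjustment; two-sided 5% (section 7.3 gives 5% but no sidedness).
- Bias in SD = imbalance x correlation.
- Standard error of the difference = sqrt(2/30) = 0.258 SD, so the shift in the test statistic = bias x sqrt(15) = bias x 3.873.
- Rejection probability = 1 - Φ(1.96 - shift) + Φ(-1.96 - shift).

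| Imbalance | Correlation | Bias (SD) | Shift | False-positive rate |
|---|---|---|---|---|
| 0.3 | 0.3 | 0.09 | 0.35 | 6.4% |
| 0.3 or 0.5 | 0.5 or 0.3 | 0.15 | 0.58 | 8.9% |
| 0.5 | 0.5 | 0.25 | 0.97 | 16.2% |

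**4. Is an adjusted comparison affordable?** With N = 60 and 6 predictors, the test of the single group coefficient has 80% power at f² = 0.136 (partial R² = 0.12). For equal groups and covariates unrelated to group, f² = d²/4, so d = 2 x sqrt(0.136) = 0.74 residual SD. An unadjusted 30 v 30 comparison has 80% power at 0.72 SD (normal approximation). Residual degrees of freedom fall from 58 to 60 - 6 - 1 = 53. So adjustment costs little in itself. Covariates that differ between the groups cost some precision; prognostic ones recover some by reducing the residual SD. Either way, only large effects are detectable.

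**The case against.** The strongest reply has five parts.

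- **Section 9 never says unadjusted.** Robust regression would fit its wording, and section 7.3 may well intend an adjusted comparison. This stands. A reader might infer that the plan prescribes an unadjusted test, or that sections 7.3 and 9 flatly contradict each other; the text supports neither. What it supports is that the protocol does not fix adjustment for this comparison.
- **Model details belong in a statistical analysis plan.** That holds for covariate coding and the handling of skewed outcomes. It does not dispose of the point: the protocol itself rules out matching, sizes the study for one analysis and words the comparison so that a simpler one complies.
- **Confounding is partly restricted already.** Both groups come from one centre, have planned surgery, share age, weight and height limits, and are subject to the same exclusions. This stands, and it lowers the likely imbalance. It does not balance severity or diagnosis within those limits.
- **The size is assumed.** This stands. With 30 v 30, a chance difference in a baseline score has a standard error of 0.26 SD, so an observed 0.3 SD would be unremarkable. The inflation above arises only if the imbalance is systematic, and 6.4% against 5% is small.
- **Adjustment is no cure-all.** This also stands. Robot patients enter on an expected ventilation time above 48 hours, controls on an actual one. That selects controls on a primary outcome, and baseline covariates cannot undo it. Also, section 8.3 classes the strength and ultrasound examinations as study-related, while control data come from routine records, so those outcomes are not shown to exist for controls.

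**Conclusion.** The point holds in a limited form. For its non-randomised comparison of patient outcomes, the protocol fixes no control of confounding: matching is excluded, the stated methods address distribution rather than imbalance, and the regression behind the sample size is not carried into the analysis of these outcomes.

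It would go too far to say that the effect estimate is biased. The protocol contains nothing from which a bias could be calculated. The false-positive rate of about 6% to 16% rests wholly on the assumed imbalance and correlation, on 30 v 30 and on no adjustment being made.

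This should be fixed before outcomes are compared, but it does not undermine the whole study. The feasibility and staff-experience arms do not depend on it, and section 10 already cautions against uncritical generalisation.

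**What to change.** In section 9, state that for outcomes available in both groups (at least ventilation time and length of stay) the effect of robot-assisted mobilisation is estimated by the multiple regression of section 7.3. The model contains treatment group plus a few prespecified baseline covariates listed in section 8.3:

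- age;
- sex;
- APACHE II or SAPS II, taken at admission;
- diagnosis or operative status, coded so that the total stays within the limit of 6 independent variables.

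Type of surgery is not a listed item, so it should not be assumed available. For skewed outcomes, use a robust or transformed version of the same model. Report the unadjusted comparison as supportive.

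Add a sentence saying that this adjustment does not remove the difference between expected (robot) and actual (historical) ventilation above 48 hours, so that conclusions on ventilation time remain limited.

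The cost is wording and a few degrees of freedom. No new data are needed, provided the routine records hold these covariates for the historical patients, which should be confirmed.

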## 10. ETHICAL CONSIDERATION FROM THE PERSPECTIVE OF THE STUDY TEAM

The study itself is designed as a clinical intervention study with comparison to a historical patient population. Patient participation is voluntary. The value of early mobilization in critically ill patients has been proven, as has the safety of early mobilization. Harmful events occurred very rarely in comparable studies, and serious adverse events seen in association with the study did not occur (5, 16). The use of the VEMO© system has also been studied and found to be safe. Thus, participating patients have no a priori disadvantage. The VEMO© system has a CE certificate and is approved for the early mobilization of critically ill patients. It is categorized as a class 2a medical device and is in regular use in several German and international hospitals, such as the Berufsgenossenschaftliche Unfallklinik Murnau, the Schön Klinik Bad Aibling or the Universitätsmedizin Charité Berlin. The system is only used for the approved indication (early mobilization of critically ill patients). A hygiene concept for the application of the system was developed in cooperation with the hospital hygiene department. The surveys within the scope of organizational feasibility accompany the interventions and pose no risk to patients through the observational function.

Otherwise, the study team has no influence on the treatment of the patients.

The primary benefit in terms of effects on patient outcomes is to determine whether robot-assisted mobilization differs from conventional early mobilization in its ability to reduce ventilation time, muscle atrophy, and intensive care unit (ICU)-acquired weakness.

Individual patients could benefit from intensive robot-assisted early mobilization in terms of shorter ventilation, less muscle atrophy, and better physical functionality. A lasting negative impact in the patient group is not expected if treatment with a safe, non-invasive medical device and intensive physiotherapeutic exercise is performed. Serious adverse events associated with the medical device are not known. Possible adverse events such as short-lasting changes in blood pressure and heart rate, the accidental removal of drains or the development of skin lesions due to the mobilization cuffs could occur.

From the data obtained, improved therapy concepts can be developed and the use of robot-assisted mobilization can be established as part of a new standard of care. This study makes a significant contribution to a future improvement of therapy for critically ill patients. If the measures of robot-assisted VEM prove to be superior to the measures of historical, conventional VEM, the new treatment technique could be quickly implemented in the clinical routine of intensive care units on the basis of the project presented here.

The data collected during the study are not available to the treating physicians during the patient recruitment phase. This way, in particular, no negative influence on the therapy of the individual patient can arise. Even if conclusions regarding the treatment of future patients or patients from other intensive care units cannot be drawn from the data obtained in an unlimited and uncritical manner, the study presented here provides a valuable gain in knowledge with the aim of comparatively examining different forms of early mobilization of the effect on a specific patients population. By simultaneously surveying the experience and behavior of the mobilizing professionals, it is also possible to record their workload when using the new therapy. Given the high workload in intensive care units, a feasibility study is essential, so the focus of this study is on users, patients, and structures.

In summary, this study makes an important and necessary contribution to improving the therapy of critically ill patients. There are no study-related burdens for the individual patients and participation in the study is without risks for the patients.

## 11. DATA MANAGEMENT (DATA PROTECTION, ANONYMIZATION, DATA STORAGE)

For the entire project, an overarching data protection statement Art 6 DSGVO of the data protection officer of the LMU Hospital is available. (Procedure number 1582 of 26.02.2020/ Procedure Number 1582a of 13.07.2021).

The data will be collected by means of digital questionnaires. The patients receive a three-digit pseudonymized ID after giving their consent. Target criteria collected in routine clinical practice will be recorded with the routine case number and transferred to the research database created specifically for the project. After completion of the documentation, the case number will be replaced by the above-mentioned ID. All personal data will be recorded under this ID. The data from the survey forms are promptly stored electronically in a secure folder. These are secured by the network of the participating institutions and the restricted access to the data.

Only the research team has access to the research database. Access to personal data (effects on patient outcomes) is restricted to the study physicians, who are bound by medical confidentiality. After completion of the study for the individual patients, the personal reference is removed and the encryption code is only kept in a written document in a lockable cabinet on the anesthesiological intensive care unit, to which only the clinical study director has access. Decoding is only done for the safety of the patients (= medical reasons) or in case of a change of the scientific question (= scientific reasons). The regulations of medical confidentiality and data protection are observed in this study. Patients will be informed in detail about data protection during the patient education. Access to study-related data is only possible via the respective study directors. All data will be destroyed according to the usual retention periods (Federal Data Protection Act).

Only the study team of the LMU Hospital and the Catholic University of Eichstätt-Ingolstadt (experience and behavior of the users) has access to the collected data.

The names of the participants and all other confidential information are subject to confidentiality and the regulations of the General Data Protection Regulation (DSGVO) and the Federal/State Data Protection Act (BDSG/BayDSG). Data of the study participants will not be passed on. Third parties will not be given access to the original documents. The data collected during the study will be kept until the data analysis is completed and then destroyed. Pseudonymized data may be shared with scientific project partners as part of the discourse on the study.

### OBLIGATION OF THE STUDY MANAGEMENT ACCORDING TO STUDY PROTOCOL

The study directors as well as all participating scientists commit themselves to conduct the study described here according to the study protocol. Changes of the study protocol are only possible after consultation with the ethics committee, if necessary a new evaluation will be obtained.

## BIOBANKING

Biobanking will not be performed in this study.

## 12. DISSEMINATION

The results of the study as well as results from the respective surveys will be made available to the public subsequently. This will be done in the form of publications.

